9.3.4. Adverse Event and Serious Adverse Event Recording and Reporting

AEs and SAEs will be recorded from signing of the ICF through completion of the Follow-up Visit. The investigator is required to record the AE or SAE regardless of the severity of the event or its relationship to study treatment. The investigator must follow up on all AEs and SAEs reported to have occurred through the Follow-up Visit until the event has resolved or stabilized or at such time the investigator refers the subject to a nonstudy physician. The investigator will document the further follow-up information in the subject's source document.

During the period specified above, the investigator will:

- Record all AEs and SAEs from the signing of the ICF through the completion of the Follow-up Visit.
- Report all SAEs on an SAE Report Form to Mallinckrodt Global Pharmacovigilance or designee.
- Report all pregnancies to Mallinckrodt Global Pharmacovigilance or designee on the appropriate form.
- Submit any Expedited Safety Report or Suspected Unexpected Serious Adverse Reaction from Mallinckrodt Global Pharmacovigilance or designee to the IRB/IEC.

The reporting requirements for AEs are summarized in the following table:

Table 5: Reporting Requirements for Adverse Events

Seriousness	Reporting Time	Type of Report
All Serious	Within 24 hours of first knowledge of event	Initial report on the SAE Form, appropriate eCRF, and source document
	Within 24 hours of receipt of follow-up information	Follow up report on the SAE Form, appropriate eCRF, and source document
Nonserious	Per case report form submission procedure	Appropriate eCRF and source document

9.3.5. Adverse Events of Special Interest

An adverse event of special interest is an event of scientific and medical concern specific to the sponsor's product or program, for which ongoing monitoring and rapid communication by the investigator to the sponsor can be appropriate. Such an event might warrant further investigation in order to characterize and understand it.

AEs of special interest for this study are outlined below. Adverse events of special interest will be followed until resolution or return to baseline.

- Increased IOP of 10 mm Hg or more from baseline confirmed upon repeat testing.
- New or worsening cataracts.
- New or worsening glaucoma.

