This is a multicenter, multiple dose, open-label study to examine the efficacy of Acthar in adult subjects 18 years of age or older with a diagnosis of keratitis sicca. Up to 36 subjects with severe or recalcitrant keratitis who did not respond or tolerate treatment with topical cyclosporine or any immunosuppressant to treat keratitis will be enrolled. Subjects who meet entry criteria will be treated with Acthar 1 mL (80 units [U]) subcutaneously (SC) 2x (twice) per week for 12 weeks. After this 12 weeks, Acthar will be tapered over 4 weeks. The 80 U dose will be reduced to 40 U 2x/week for 2 weeks, followed by 40 U 1x/week for 2 additional weeks. Subjects will be reassessed at an in-clinic

Study Title: A Multicenter, Open-label Study to Assess the Efficacy and Safety of Acthar® Gel in Subjects with Severe Keratitis

Protocol Number: MNK14084113 Type: Interventional/Phase 4

Condition/Disease: Severe or Recalcitrant Keratitis

safety visit, 4 weeks after the last treatment dose for AE assessments and concomitant medication use. Endpoints will be measured at Baseline (Visit 2 [Day 1]), and Visit 3 through 6.

Number of Subjects:

Up to 36 subjects will be enrolled in this study at approximately 6 sites in the US.

Treatment Groups and Duration:

Subjects with severe or recalcitrant keratitis who did not respond or tolerate treatment with topical cyclosporine or any immunosuppressant to treat keratitis will be enrolled. Subjects will participate in the study for approximately 22 weeks, including a screening period of up to 28 days, an active treatment period of 12 weeks, an Acthar taper period of 4 weeks, and a follow up in-person safety visit 4 weeks after the last dose of study drug.

SCHEDULE OF STUDY EVENTS

Table 1: Schedule of Study Events

Study procedures	Visit 1 Screening Day -28 to-1	Visit 2 Baseline Day 1	Visit 3 Phone Day 15 ±1	Visit 4 In Clinic Day 29 ±2	Visit 5 In Clinic Day 43 ±2	Visit 6 In Clinic Day 85 ±3	Visit 7 In Clinic / End of Acthar Taper Day 113 ±3	Early Termination
Informed consent	X							
Urine pregnancy test	X							
Demographic data, medical, surgical, ophthalmic history	X							
Patient-Reported Outcomes								
ODS	X	X		X	X	X		X
IDEEL and VAS		X	X	X	X	X		X
Ophthalmic examination								
Visual Acuity	X	X		X	X	X	X	X
Slit Lamp Evaluation	X	X		X	X	X	X	X
Conjunctival redness	X	X		X	X	X		X
Tear film breakup time	X	X		X	X	X		X
Inferior corneal staining score	X	X		X	X	X		X

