Study procedures	Visit 1 Screening Day -28 to-1	Visit 2 Baseline Day 1	Visit 3 Phone Day 15 ±1	Visit 4 In Clinic Day 29 ±2	Visit 5 In Clinic Day 43 ±2	Visit 6 In Clinic Day 85 ±3	Visit 7 In Clinic / End of Acthar Taper Day 113 ±3	Early Termination
Superior, central and total corneal staining score (fluorescein)	X	X		X	X	X		X
Nasal, temporal and total conjunctival staining score (lissamine green)	X	X		X	X	X		X
Schirmer's Test	X	X		X	X	X		X
IOP	X					X	X	X
Undilated Fundoscopy	X					X	X	X
Inclusion/Exclusion criteria review	X	X						
Height ^a and weight	X	X				X	X	X
Vital signs ^b	X	X		X	X	X	X	X
Physical examination	X					X		X
Laboratory testing								
Chemistry and others ^c	X	X		X	X	X		X
HbA1c	X	X		X	X	X		X
Serum Pregnancy	X	X		X	X	X		X

Study procedures	Visit 1 Screening Day -28 to-1	Visit 2 Baseline Day 1	Visit 3 Phone Day 15 ±1	Visit 4 In Clinic Day 29 ±2	Visit 5 In Clinic Day 43 ±2	Visit 6 In Clinic Day 85 ±3	Visit 7 In Clinic / End of Acthar Taper Day 113 ±3	Early Termination
Hepatitis Serology ^d	X							
IGRA for TB	X							
Immunological protein assay ^e	X	X				X		X
IXRS contact	X	X		X	X			X
Study Therapy								
Study drug and injection record training		X						
Dispense study drug		X		X	X			
Administer first dose in clinic ^f		X						
Adverse event assessment	X	X	X	X	X	X	X	X
Injection record review				X	X	X	X	X
Concomitant treatment review		X	X	X	X	X	X	X
Start Acthar Taper						X		
End Acthar Taper							X	
Study exit							X	X

AE = adverse events; ET = early termination; HbA1c = glycosylated hemoglobin; IDEEL = Impact of Dry Eye on Everyday Life; IGRA = Interferon gamma release assay; IOP = Intraocular Pressure; ODS = Ocular Discomfort Score; TB = tuberculosis; VAS = Visual Analogue Scale.

^a Height at screening only. Weight at screening, Visits 2, 6, and ET.

^b Blood pressure, respiratory rate, pulse rate and body temperature. For blood pressure, an average of 2 readings after the subject has been seated for \geq 5 minutes at the Screening and Baseline Visits. Single readings after subject has been seated for \geq 5 minutes at all other time points.

^c Refer to Section 9.2.

^d HBsAg, HBcAb, and HCV.

^e Refer to Table 2.

^f The first dose will be administered at the clinic and the subject should be observed for at least 1 hour after dosing.

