1.3. Assessment of Potential Benefits and Risks

Common adverse reactions for Acthar include fluid retention, alteration in glucose tolerance, elevation in blood pressure, behavioral and mood changes, increased appetite, and weight gain.

Prolonged use of Acthar may produce posterior subscapular cataracts, glaucoma with possible damage to the optic nerves, and may enhance establishment of secondary ocular infections due to fungi and viruses. For a complete reference of known potential risks, refer to the [**Acthar® Gel Package Insert, 2019**](#). More detailed information about the known and expected benefit, risks, and reasonably expected adverse events (AE) can be found in the Acthar® Gel Package Insert, 2019.

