3. STUDY DESIGN

3.1. Overall Design

This is a multicenter, multiple dose, open-label study to examine the efficacy of Acthar in adult subjects 18 years of age or older with a diagnosis of keratitis sicca. Up to 36 subjects with severe or recalcitrant keratitis who did not respond or tolerate treatment with topical cyclosporine or any immunosuppressant to treat keratitis will be enrolled. Subjects who meet entry criteria will be treated with Acthar 1 mL (80 units [U]) subcutaneously (SC) 2x (twice) per week for 12 weeks, followed by a 4 week taper period of 40 U 2x/week for 2 weeks then 40 U 1x/week for 2 more weeks. Subjects will be reassessed at an in-clinic safety visit, 4 weeks after the last treatment dose for AE assessments, and concomitant medication use. Endpoints will be measured at Baseline and all other visits.

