7.1.1. Ophthalmic Examination

An ophthalmic examination will be completed at specified times during the study and will include the following:

- Best corrected visual acuity (BCVA) measured using the using the Early Treatment Diabetic Retinopathy Study (ETDRS) chart ([Hilton, 2009](#)).
- Intra-ocular pressure (IOP) will be measured using Goldmann Applanation Tonometry ([Ramakrishnan, 2009](#)).
- Complete Slit lamp examination (including evaluation of the cornea and lens and grading of superficial puncta).
- Undilated funduscopic evaluation.

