7.2. Safety Assessments

All safety assessments will be performed at times outlined in the Schedule of Study Events ([Table 1](#)). Safety assessments that will be evaluated include adverse events, ophthalmic examinations, physical examination, clinical laboratory test results, metabolic panel, pregnancy testing, and vital signs.

Additional (unscheduled) safety assessments may be performed as needed.

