8.3.2. Safety Analyses

All safety data will be summarized with descriptive statistics or frequency tables as appropriate. Safety analyses will be performed on the safety population. Safety endpoints include the incidence and severity of ocular AEs, incidence and severity of other AEs, new or worsening cataracts, and the mean change in IOP.

AEs will be coded using MedDRA version 22.0 by preferred term within system organ class. The number of AEs and the number of subjects reporting AEs will be listed and summarized descriptively by system organ class, preferred term, severity, and causality for each treatment group. Only treatment-emergent adverse events (TEAE) (events that are new in onset or aggravated in severity following treatment) will be included in all summaries. Serious adverse events (SAE) (including death) will be summarized.

Other safety assessments include vital signs (heart rate, diastolic/systolic blood pressures, respiratory rate, and body temperature), clinical laboratory tests, ophthalmology examinations, physical examinations, HbA1c, pregnancy test, hepatitis serology, IGRA for TB, etc. All of these assessments will be listed and summarized descriptively.

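### The IOP event of special interest is a rise from baseline, yet no IOP reading is scheduled on Day 1 or, early termination aside, on treatment before Day 85

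*Combined protocol and SAP*

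**What the plan says.** Section 9.3.5 lists three AESIs: new or worsening cataracts, new or worsening glaucoma, and "Increased IOP of 10 mm Hg or more from baseline confirmed upon repeat testing". It also has AESIs followed until they resolve or return to baseline, so the reference value is used twice. Section 8.3.2 includes "new or worsening cataracts, and the mean change in IOP" among the safety endpoints. The reason for watching pressure is in Section 1.3: "Prolonged use of Acthar may produce posterior subscapular cataracts, glaucoma with possible damage to the optic nerves".

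On timing, the Synopsis says "Endpoints will be measured at Baseline (Visit 2 [Day 1]), and Visit 3 through 6", and Section 3.1 says "Endpoints will be measured at Baseline and all other visits". Section 7.2 is specific to safety: "All safety assessments will be performed at times outlined in the Schedule of Study Events". It adds that unscheduled safety assessments may be done if needed.

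The IOP row of Table 1 is marked at Screening, Visit 6, Visit 7 and early termination (ET), and is blank at Visits 2 to 5. The next row, "Undilated Fundoscopy", has the same pattern. The method is already fixed in Section 7.1.1: IOP "will be measured using Goldmann Applanation Tonometry". No section defines baseline for IOP.

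**The concern.** An event defined as a change from baseline needs a clear reference value and follow-up readings at times when the event could occur. The plan is weak on both.

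The Synopsis equates Baseline with Visit 2, but no IOP is taken there. The only scheduled pre-dose value is from Screening, up to 28 days earlier, and nothing names it as the reference.

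The larger problem is follow-up. No IOP is scheduled while subjects receive 80 U twice a week, unless they terminate early. The first on-treatment reading coincides with the start of the taper, too late to affect any full-dose injection. Visual acuity and slit lamp are done on Days 29 and 43, but neither measures pressure, so a rise without symptoms has nothing scheduled to reveal it. Two things are at stake: timely detection of a risk the sponsor itself singled out, and an AESI count that may be too low by an unknown amount.

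**Working it through.** The plan gives no figure of its own on this point, so the check is a reading of Table 1 followed by arithmetic on days and dose.

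**1. Table 1, IOP against neighbouring rows (X = marked)**

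| Visit | Nominal day | IOP | Fundoscopy | Slit lamp, acuity | Schirmer |
|---|---|---|---|---|---|
| 1 Screening | -28 to -1 | X | X | X | X |
| 2 Baseline | 1 | – | – | X | X |
| 3 Phone | 15 | – | – | – | – |
| 4 Clinic | 29 | – | – | X | X |
| 5 Clinic | 43 | – | – | X | X |
| 6 Clinic | 85 | X | X | X | X |
| 7 Clinic | 113 | X | X | X | – |
| ET | – | X | X | X | X |

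The Schirmer row directly above IOP is marked at Visits 2, 4 and 5, so the blanks in the IOP row are not a column shift from text extraction. Of the two on-treatment clinic visits before Day 85, none includes IOP.

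**2. Time to the first on-treatment reading**

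- First dose to Visit 6: 85 − 1 = 84 days (81 to 87 with the ±3-day window).
- First dose to end of taper: 113 − 1 = 112 days. Share elapsed: 84/112 = 75%.
- Screening reading to Day 85 reading, with no Day 0: at most 28 + 84 = 112 days and at least 1 + 84 = 85 days, nominal.

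**3. Planned exposure before that reading (Section 5.1)**

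- Full dose: 2 × 12 = 24 injections; 24 × 80 U = 1,920 U.
- Taper: (2 × 2) + (1 × 2) = 6 injections; 6 × 40 U = 240 U.
- Injections: 24/(24 + 6) = 80%. Dose: 1,920/(1,920 + 240) = 1,920/2,160 = 89%.

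These percentages describe one fact, a first reading at Day 85, in different units. They are not separate pieces of evidence.

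**4. Effect of adding IOP on Days 1, 29 and 43**

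- Current on-treatment gaps, counted from Day 1: 84 and 28 days; longest 84.
- Revised gaps: 28, 14, 42 and 28 days; longest 42.
- Extra scheduled readings: 3 × 36 = 108 at most.

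**5. Illustration under stated assumptions**

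The documents give neither the rate of IOP rises nor how long they last. Suppose onset is uniform over the 84 days from Day 1 to Day 85 and there are no ET or unscheduled readings. For scheduled gaps g, a rise lasting D days is caught with probability Σ min(D, g)/84, and the mean delay to the first check of a persistent rise is Σ g²/(2 × 84).

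| Quantity | Current (g = 84) | Revised (g = 28, 14, 42) |
|---|---|---|
| 14-day rise caught | 14/84 = 17% | (14 + 14 + 14)/84 = 50% |
| 28-day rise caught | 28/84 = 33% | (28 + 14 + 28)/84 = 83% |
| Mean delay, persistent rise | 7,056/168 = 42 days | (784 + 196 + 1,764)/168 = 16.3 days |

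The durations and the uniform onset are assumptions. Without them, the share of qualifying rises missed equals the share that resolves before Day 85 with no ET or unscheduled reading, which could be anything from none to all.

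**The case against.** The case for leaving the schedule alone has several parts.

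- **Reference value.** Screening is the only scheduled pre-dose reading, so it is the natural baseline and a change can be computed. Section 7.2.2 already uses Screening as the reference for the physical examination, and the separate SAP promised in Section 8.3 could supply the definition. This largely stands: what is missing is a definition and a fresher value, and the endpoint is still usable. It does not affect the 84-day on-treatment gap.
- **Timing sentences.** Those in the Synopsis and Section 3.1 cannot be literally true, since Visit 3 is a phone contact, and Section 7.2 settles the conflict in favour of Table 1. That is right, and it confirms that sites following the protocol would not measure IOP on Days 1, 29 or 43.
- **Missed events.** A missed event needs a rise that resolves while the dose is unchanged, and nothing in the documents suggests that course. Section 1.3 speaks of prolonged use, and Day 85 falls at the end of full dosing. This is fair: late detection is the better-supported harm, and missed transient rises are a possibility of unknown size.
- **Safeguards.** Glaucoma is among the conditions covered by exclusion 2, other corticosteroids are restricted, adverse events are assessed at every visit, and unscheduled checks are allowed. These reduce the risk, but none would reveal a silent rise before Day 85.
- **Context.** This is a small, open-label Phase 4 study of a product labelled for keratitis, with descriptive safety analysis, and no document sets a required IOP interval. The preferred spacing is therefore a judgement. Even so, the sponsor made the IOP rise an AESI and describes AESIs as events that can call for ongoing monitoring. It follows HbA1c and blood pressure at Visits 2, 4, 5 and 6, but not IOP.

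**Conclusion.** The concern holds. Followed as written, the protocol takes no IOP reading at its Baseline visit and, ET aside, no scheduled on-treatment reading until 84 days, 24 injections and 1,920 U have passed. A rise that begins during full dosing may be found late. One that resolves first may not be found at all, so the AESI count could be too low. The timing follows directly from Table 1 and Section 5.1, using nominal visit days and full adherence. The number of events delayed or missed cannot be derived from the documents, and the percentages in the illustration depend on assumed onset and duration. The unclear reference value is a lesser, separate point. This is a design choice that should be changed because the improvement is cheap; it does not invalidate the study.

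**What to change.** Mark IOP in Table 1 at Visit 2 (before the first dose), Visit 4 and Visit 5, and define the IOP baseline as the last value before the first dose. Take the reading after staining and Schirmer's test so that those measures are not disturbed.

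The cost is three table marks and one definition: 3 readings per subject, at most 108 for 36 subjects, not counting confirmatory repeats. They use tonometry already specified, at clinic visits that already include a slit lamp examination. The downsides are slightly longer visits and a few more contact readings on inflamed corneas. A 42-day gap remains between Days 43 and 85.

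If the sponsor keeps the present schedule, the minimum is a change of wording. Name the Screening value as the IOP reference, and limit the endpoint-timing sentences in the Synopsis and Section 3.1 to what Table 1 marks. Then report the AESI as rises observed at Day 85, Day 113, ET or unscheduled checks, not as incidence over the treatment period. That makes the report accurate but does not bring detection forward.

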9.4. Appendix 4: Pregnancy Reporting

Certain information regarding pregnancy, although not considered an SAE, must be recorded, reported, and followed up as indicated. This includes the following:

Subjects should not become pregnant during the study. If a female subject, or the female partner of a male subject, becomes pregnant during any active treatment period, study treatment must be discontinued immediately and the investigator must report the pregnancy by submitting the appropriate form to Mallinckrodt Global Pharmacovigilance, or designee, within 24 hours of confirmation of a pregnancy (ie, positive serum pregnancy test result). The outcome of pregnancy (eg, spontaneous abortion, live birth, still birth, congenital anomalies, birth defects) must be reported by submitting the appropriate form to Mallinckrodt Global Pharmacovigilance,

or designee, within 24 hours of the pregnancy outcome being submitted to the study site. If the pregnancy results in a live birth, a postdelivery follow-up will be performed at least 28 days after the baby is born and must be reported to Mallinckrodt Global Pharmacovigilance, or designee, within 24 hours of the study site becoming aware of the follow-up information.

9.5. Appendix 5: Liver Safety: Suggested Actions and Follow-up Assessments

All events of alanine aminotransferase (ALT) $\geq 3 \times$ upper limit of normal (ULN) and with total bilirubin $\geq 2 \times$ ULN ($> 35\%$ direct bilirubin) or ALT $\geq 3 \times$ ULN and international normalized ratio (INR) > 1.5 (if INR measured) which may indicate severe liver injury (possible Hy's Law) must be reported as an SAE as outlined in Section 9.3.4.

Subjects with confirmed Hy's Law liver injury will be immediately withdrawn from study treatment and no rechallenge will be allowed.

